1.0 Objectives

1.1 Primary Objectives: To evaluate the objective response rate of low dose of inotuzumab ozogamicin as measured by the hematologic remission rate (CR + CR_p + CR_i) in patients in first, second or later salvage setting.

1.2 Secondary Objectives: To evaluate the overall safety profile and the efficacy; the efficacy is measured by the hematologic response rate (CR + CR_i + PR), durations of response (DoR) and remission (DoR1), progression free survival (PFS), and overall survival (OS)

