3.2 All patients will be registered through CORe

3.3 Patients will receive inotuzumab ozogamicin at the dose of 0.8 mg/m² on Day 1 (+/- 3 days), and 0.5 mg/m² on Days 8 and 15 (+/- 3 days) of cycle 1. Subsequent cycles will consist of inotuzumab ozogamicin at the dose of 0.6 mg/m² on Day 1 (+/- 3 days) and 0.3 mg/m² on Day 8 (+/- 3 days). Patients will have a bone marrow aspiration performed on Day 14 and Day 21 (+/- 3 days). If marrow aspiration shows no disease, Cycle 2 could resume on Day 28 (+/- 7 days) at the dose level recommended in section 8.1.6. If persistence disease (defined by bone marrow blasts >5%), Cycle 2 would resume as early as Day 22 (+/- 7 days). Responding (CR, CRi, CRp) patients could receive up to 5 additional cycles. A maximum of 6 cycles will be administered.

3.4 In patients with an allogeneic donor, an allogeneic stem cell transplantation will be offered at any time after the first cycle of treatment with inotuzumab ozogamicin. Cycles are to be repeated every 3 to 4 weeks.

3.5 Responders will be permitted to receive up to five additional consolidation cycles of treatment with inotuzumab ozogamicin.

3.6 CSF prophylaxis consisting of an intrathecal regimen according to institutional guidelines during and after inotuzumab treatment will be left to the investigator's discretion.

3.7 Patients who relapse after achieving a response for at least 3 months can be retreated for up to 6 additional cycles.

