5.0 Evaluation During Study

Procedure	Comments	Schedule
Hematology	CBC with differential and platelet count	Weekly during cycles 1 to 6
Biochemistry	at least creatinine, total bilirubin, SGPT or SGOT	Cycle 1, prior to study drug infusion Cycle 2-6, prior to each study drug infusion and/or at the discretion of the treating physician.
Physical Examination	Focused physical examination	Prior to each treatment cycle
Bone marrow	Aspirate and/or biopsy (MRD) by flow multicolor cytometry and by polymerase chain reaction (PCR).	On day 14, 21 +/- 3 days of the first cycle, then every 2-3 cycles.

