5.1 Follow-up

Patients will be followed up to 30 days after completion of treatment. Afterward they may be enrolled and followed for survival under protocol DR09-0223.

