7.0 Background

7.1 Salvage therapy in acute lymphoblastic leukemia (ALL).

Despite an exceptionally high rate of initial CR, many adults with ALL will relapse. Current strategies to induce a second remission translating into long-term survival are lacking. Cytotoxic chemotherapy results in modest CR rates of 30-40% in first salvage and 10-20% in later salvages. Few patients can be bridged to allo-SCT, 5-10% in some studies but as high as 30-40% in the German trials^{1,2}. This bridging to allo-SCT offers a chance of long term remissions and cures (<20-30%). One of the most exciting groups of compounds under investigation in relapsed refractory (R/R) ALL are monoclonal antibodies

targeting CD19 and CD22. Of these antibodies, blinatumomab and inotuzumab ozogamicin are in the most advanced investigational phases (Table 1).

Blinatumomab was granted FDA approval for the treatment of R/R ALL in December 2014. Furthermore, inotuzumab was found to be superior to best available therapy in a randomized trial in patients with R/R ALL and was granted FDA approval for the treatment of R/R B-cell precursor ALL in August 2017.

The randomized trial confirmed the findings of the initial phase II studies. Inotuzumab induces responses in 80% of the patients with a median survival of 7.7 months. The rate of VOD was 10%. The aim of this study is to reduce the rate of VOD without minimizing efficacy.

Table 1. Monoclonal antibodies in relapsed/refractory ALL

Parameter	N (%)			
	Blinatumomab		Inotuzumab	
	Pivotal Study, n=36	Confirmatory Study, n=189	Single dose n=49	Weekly n=40
Overall Response	25 (69)	81 (43)	28 (57)	24 (60)
Salvage Status				
Salvage 1	11 (31)	38 (20)	13 (27)	16 (40)
Salvage 2+	10 (28)	151 (80)	36 (73)	24 (60)
Median survival (months)	9.8	6.1	5.0	9.5

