The hematologic remission rate will be estimated along with the 95% credible interval. Data from all subjects who receive any study drug will be included in the safety analyses. Subjects who entered the study but did not take any of the study drug and had this confirmed will not be evaluated for safety. The severity of the toxicities will be graded according to the NCI CTCAE v4.03 whenever possible. We will follow standard reporting guidelines for adverse events. Safety data will be summarized by AE category, severity and frequency. The proportion of patients with AEs will be estimated, along with the Bayesian 95% credible interval. Kaplan-Meier method will be used to assess the overall survival (OS), progression-free survival (PFS), duration of response (DoR) and durations of remission (DoR1). The rate of hematologic response (CR + CRI + PR) will also be estimated.

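### Required follow-up ends 30 days after treatment and no later relapse assessment is described, so Kaplan-Meier DoR, DoR1 and PFS are cut short and OS rests on optional enrolment elsewhere

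*Combined protocol and SAP*

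**What the plan says.** Section 1.2 lists as secondary efficacy measures the "durations of response (DoR) and remission (DoR1), progression free survival (PFS), and overall survival (OS"). Section 11.0 commits to Kaplan-Meier for all four: "Kaplan-Meier method will be used to assess the overall survival (OS), progression-free survival (PFS), duration of response (DoR) and durations of remission (DoR1"). It gives no event definition, time origin, censoring rule or data cut-off, and it does not say how transplant is handled.

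Section 5.1 sets the follow-up: "Patients will be followed up to 30 days after completion of treatment". What comes next is permissive and concerns survival: "Afterward they may be enrolled and followed for survival under protocol DR09-0223". Section 11.0 does not name that protocol as a data source.

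The marrow schedule in section 5.0 is tied to cycles: "On day 14, 21 +/- 3 days of the first cycle, then every 2-3 cycles". No marrow or other relapse assessment is scheduled after treatment.

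Time on treatment varies with the patient's course. Responders may have up to 6 cycles (3.3). Non-responders come off after 2, or up to 4 by exception (10.1). For patients with a donor, "an allogeneic stem cell transplantation will be offered at any time after the first cycle of treatment with inotuzumab ozogamicin" (3.4), and section 8.3 recommends about 2 cycles, or the fewest needed for remission, before a planned transplant. Section 3.7 adds: "Patients who relapse after achieving a response for at least 3 months can be retreated for up to 6 additional cycles".

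**The concern.** A duration endpoint needs disease status to be known for long enough to see a fair share of the relapses. Here the required observation ends shortly after the last cycle, and the optional follow-up that comes after is described only for survival. As described, it can supply OS but not DoR, DoR1 or PFS.

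The observation time is also unequal. For DoR and DoR1 it depends on the number of cycles and on transplant. For PFS and OS it depends on response as well. Patients who stop early for transplant have the shortest window, and that route is not rare: in the single-dose study in section 7.3.1, 22 of 49 patients (45%) went on to transplant.

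At stake is half of the trial's own question. Section 7.1 gives the aim as lowering the VOD rate without giving up efficacy. Durability belongs to efficacy, and under this plan it can hardly be judged beyond the treatment period.

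**Working it through.** The plan states no figure for these four endpoints, so there is none to reproduce. The check asks how long required follow-up lasts and what share of relapses could fall inside it.

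**Inputs from the documents.** Cycle length 21-28 days (3.4, 8.1.3); at most 6 cycles (3.3); 30 days after treatment (5.1); delays of more than 28 days between cycles end treatment (8.1.5); median response duration 4.6 months with inotuzumab in the randomized trial (7.3.1); median survival 7.7 months (7.1).

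**Assumptions.** Exponential times; response on day 21; completion of treatment means the end of the last cycle; every relapse inside the window is detected; 30.44 days per month. The medians come from standard-dose inotuzumab, not from this schedule.

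**Step 1: required follow-up = cycles × cycle length + 30 days.**
- 2 cycles: 42 + 30 = 72 to 56 + 30 = 86 days (2.4-2.8 months).
- 4 cycles: 84 + 30 = 114 to 112 + 30 = 142 days (3.7-4.7 months).
- 6 cycles: 126 + 30 = 156 to 168 + 30 = 198 days (5.1-6.5 months).
- 6 cycles with a 28-day delay before each of cycles 2 to 6: 198 + 5 × 28 = 338 days (11.1 months).

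**Step 2: DoR window = (follow-up − 21) / 30.44.**
- 2 cycles: 51/30.44 = 1.68 to 65/30.44 = 2.14 months.
- 6 cycles: 135/30.44 = 4.43 to 177/30.44 = 5.81 months.

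**Step 3: share of relapses inside the window = 1 − 0.5^(window/4.6).**
- 2 cycles: 0.223 to 0.275.
- 6 cycles: 0.487 to 0.584.

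**Step 4: responders without an observed relapse, if a share q stops after 2 cycles for transplant and the rest have 6 cycles.** The formula is 1 − [q × seen(2) + (1 − q) × seen(6)].
- q = 0: 1 − 0.487 = 0.513 to 1 − 0.584 = 0.416.
- q = 0.4: 1 − (0.4 × 0.223 + 0.6 × 0.487) = 0.618 to 1 − (0.4 × 0.275 + 0.6 × 0.584) = 0.540.

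With 24 responders (50% of 48) that is about 10-12 and 13-15 patients.

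**Step 5: sensitivity.**
- q = 0.8 gives 66-72%. This is near the most that the single-dose study allows: 22 transplants among 28 responders (9 + 16 + 3 in Table 2) would be 79% if every transplanted patient was a responder.
- Maximum delays and no transplant: window 317/30.44 = 10.41 months, seen 0.792, so 21% without an observed relapse.
- If the 30 days run from the last (day 8) dose, follow-up is 58-65 days after 2 cycles and 142-177 after 6. The 6-cycle DoR window is then 121/30.44 = 3.98 to 156/30.44 = 5.12 months, and 46-55% have no observed relapse even with no transplant.

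**Step 6: OS within this protocol alone.** Section 7.1 says: "Inotuzumab induces responses in 80% of the patients with a median survival of 7.7 months". With that median, 1 − 0.5^(5.12/7.7) = 0.37 to 1 − 0.5^(6.50/7.7) = 0.44 of deaths fall inside the longest undelayed window. The rest of the OS curve depends on how many patients enter DR09-0223, which the documents do not say.

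**Step 7: does short follow-up imply bias?** Take 44% of responders transplanted and last observed 58 days into response, the others observed to 170 days (28-day cycles, response at day 28). The Kaplan-Meier estimate of 5-month DoR is then 0.47 whatever happens after transplant. The true value is 0.525, 0.47 or 0.43 if the relapse hazard after transplant is 0.5, 1.0 or 1.5 times that of the others (assumed ratios). The error runs from about 5 points too low to about 4 points too high, and it is nil when transplant does not change relapse risk.

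**The case against.** The best counter-argument is section 3.7. Retreatment after a relapse that follows at least 3 months of response, with no time limit, presupposes that the investigators will learn of later relapses. That is fair, and in practice some relapse dates will be known. But the clause sets no schedule and no duration, and it covers only patients who come back. Safety reporting does not fill the gap: sections 12.0 and 12.1 record events to 30 days after the last dose and, after that, only treatment-related serious events.

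Second, no text says that patients are censored at transplant or at day 30. This also stands. The cut-off is inferred, because treatment stops, so the 30-day clock starts, when a patient leaves for transplant. A reader might go further and call the censoring of DoR and DoR1 response-dependent. That cannot be right, since every patient in those analyses is a responder.

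Third, DR09-0223 is not among the documents. Enrolment may be routine, and it may record relapse. A reader might infer that OS will be unusable; the documents do not support that, because OS could be well estimated if uptake is good. What can be said is that this protocol neither requires the enrolment nor names the data.

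Fourth, maximum delays stretch follow-up to about 11 months. That is true for a patient delayed before every cycle, but it is not a plan for follow-up.

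Finally, these are descriptive secondary endpoints with no target or test in section 11.0. That limits the severity but does not remove the gap.

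**Conclusion.** The concern holds as one of short and unequal follow-up. Followed as written and without delays, required observation ends 72-86 days after the start for a patient with 2 cycles and 156-198 days for one with 6. Under an exponential DoR with a 4.6-month median and response on day 21, roughly half of responders (42-51%) would have no observed relapse with no early transplant exits, rising to 54-62% if 40% leave after 2 cycles. These shares rest on a median from standard-dose treatment and would shift if durability at the lower dose differs.

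It is tempting to conclude that the Kaplan-Meier estimates are biased, or to name a direction. The documents do not support this: the answer depends on how transplanted patients fare, and section 7.3.1 reports similar survival with and without transplant in one earlier study. OS depends on the completeness of DR09-0223 enrolment, which is unknown.

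The primary endpoint, remission at any time during treatment, is unaffected, and so are the two-stage rule and the VOD stopping rule. This is a change that should be made because it is cheap, not a fault that undermines the trial's main result.

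**What to change.** In section 5.1, require relapse or progression, transplant and survival status for every treated patient to a common data cut-off, including after transplant, new therapy or removal from treatment. Periodic chart review or phone contact is enough; the investigators can choose the interval. This can be done on this protocol, or by making DR09-0223 entry routine, adding relapse status to it, and naming it in section 11.0 as a data source.

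In section 11.0, censor OS at last contact, and DoR, DoR1 and PFS at last disease assessment. Report DoR, DoR1 and PFS with and without censoring at transplant.

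The cost is a protocol amendment, status checks on up to 48 patients and a later data cut for the secondary endpoints. No patients or protocol marrows are added. Relapse dates taken from routine care will be less precise than scheduled marrows would give, and the report should say so.

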6.0 Criteria for Response

Complete remission (CR):

Normalization of the peripheral blood and bone marrow with 5% or less blasts with a granulocyte count of $1 \times 10^9/L$ or above and a platelet count of $100 \times 10^9/L$ or above and absence of extramedullary disease.

Complete remission without platelet recovery (CRp):

As above except platelets $< 100 \times 10^9/L$

Complete remission with incomplete count recovery (CRI):

CR without recovery of neutrophils or platelet counts

Partial response (PR):

As above, except for the presence of 6-25% marrow blasts.

MRD negativity:

MRD levels will be continuously assessed during induction and consolidation therapy by 6-color multiparameter flow. MRD negativity will be defined by a value of no more than 10^{-4} and confirmed on a second bone marrow aspiration/biopsy performed after a subsequent cycle.

No response (NR):

Patients will be considered non-responders if no response is achieved after 2 cycles.

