11.0 STATISTICAL CONSIDERATIONS

This is a single-arm phase II study of a single agent of low dose inotuzumab ozogamicin in adult patients with relapsed or refractory CD22-positive ALL. Patients will receive inotuzumab ozogamicin for up to 6 cycles. The primary endpoint of this study is hematologic remission, defined as CR + CRp + CRI occurred any time during the treatment. The Simon's optimal two-stage design will be used for interim futility monitoring. The null hypothesis is that the hematologic remission rate is 35% and our target rate under the alternative hypothesis is 50%. Under the design, we will enroll 18 patients in the first stage. If 6 or fewer patients achieve the primary endpoint, enrollment of future patients will be halted. If 7 or more out of the first 18 patients have met the primary endpoint, accrual will continue until a total of 48 patients are enrolled. If 21 or more out of these 48 patients achieve the primary endpoint, the treatment will be

considered efficacious and is worth further investigation. Under this Simon's optimal two-stage design, the type I error is 0.113, the power is 78.3%, the probability of early termination is 0.549 if the true hematologic remission rate is 35% and the expected sample size is 31.5 patients. After the first stage, if not at least 7 responders are observed in the first 18 patients, we will temporarily suspend the accrual until enough number of responders (i.e., $>/=7$) is reached.

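### The secondary hematologic response rate is written as CR + CRi + PR and leaves out CRp, which the rest of the protocol counts as remission and response

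*Combined protocol and SAP*

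**What the plan says.** The secondary rate is defined twice, each time without CRp:

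- Section 1.2: "the efficacy is measured by the hematologic response rate (CR + CR_i + PR").
- Section 11.0, Analysis Plan: "The rate of hematologic response (CR + CRI + PR) will also be estimated".

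Elsewhere CRp counts as remission or response:

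- Section 1.1 sets out to evaluate the "objective response rate of low dose of inotuzumab ozogamicin as measured by the hematologic remission rate (CR + CR_p + CR_i").
- Section 11.0 takes hematologic remission as the primary endpoint, "defined as CR + CRp + CRI occurred any time during the treatment". In the interim rule it calls patients who meet that endpoint responders: "if not at least 7 responders are observed in the first 18 patients".
- Section 3.3: "Responding (CR, CRi, CRp) patients could receive up to 5 additional cycles".
- Section 8.3 groups CR, CRi and CRp as a single level of achievement.

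Section 6.0 gives CRp its own heading, as CR except for platelets below 100 × 10⁹/L. It defines CRi as "CR without recovery of neutrophils or platelet counts". PR is the category with 6–25% marrow blasts.

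**The concern.** A response rate that adds PR to remission should never be smaller than the remission rate. With CRp and CRi as separate codes, the written formula breaks that ordering. A patient with up to 25% marrow blasts (PR) counts as a response, while a patient with 5% or fewer blasts whose platelets alone have not recovered (CRp) does not. No section gives a reason for the omission, so it looks like a drafting slip.

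Two things are at stake. First, two analysts following the same document could report very different secondary rates. Second, a rate without CRp would not be comparable with the earlier single-agent response rates that the protocol cites, which include CRp. Duration of response may inherit the problem, because the documents do not say which patients form its responder set.

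**Working it through.** **Inputs.** Table 2 (section 7.3.1) gives these counts from the earlier studies:

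| | Single-dose, n=49 | Weekly, n=40 | Overall, n=89 |
|---|---|---|---|
| CR | 9 | 8 | 17 |
| CRp | 16 | 13 | 29 |
| CRi, marrow CR | 3 | 3 | 6 |
| PR | 0 | 0 | 0 |
| Resistant | 18 | 14 | 32 |
| Death < 4 weeks | 3 | 2 | 5 |

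**Step 1: are the Table 2 categories disjoint?** The columns sum to 9+16+3+0+18+3 = 49, 8+13+3+0+14+2 = 40 and 17+29+6+0+32+5 = 89. Each equals its denominator, so each patient appears once and CRp is separate from CRi.

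**Step 2: reproduce the protocol's own response figures.** Table 1 gives overall response as 28 (57%) single-dose and 24 (60%) weekly.

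- With CRp: 9+16+3+0 = 28, and 28/49 = 57.1%; 8+13+3+0 = 24, and 24/40 = 60.0%. Both match Table 1.
- Without CRp: 12/49 = 24.5% and 11/40 = 27.5%. Neither matches.

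Section 7.3.1 quotes 57% and 59% in its text. The first agrees with 28/49. The second is one point from Table 1 and far from 27.5%. PR is 0 throughout, so the match to Table 1 depends on counting CRp.

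**Step 3: size of the omission under separate coding.**

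| Cohort | CR + CRi + PR (as written) | CR + CRp + CRi + PR | Difference |
|---|---|---|---|
| Single-dose | (9+3+0)/49 = 24.5% | 28/49 = 57.1% | 16/49 = 32.7 points |
| Weekly | (8+3+0)/40 = 27.5% | 24/40 = 60.0% | 13/40 = 32.5 points |
| Overall | (17+6+0)/89 = 25.8% | 52/89 = 58.4% | 29/89 = 32.6 points |

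CRp was the largest remission category, 29 of 52 (55.8%).

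**Step 4: when does response fall below remission?** With disjoint codes, (CR + CRi + PR) − (CR + CRp + CRi) = PR − CRp. The written response rate is below the remission rate whenever there are more CRp than PR patients. In Table 2 that is 16 against 0 and 13 against 0.

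**Step 5: illustration at this trial's size.** Assume 24/48 remissions (the 50% target), the Table 2 overall CRp share of 29/52, and no PR. The written formula then gives 24 × (1 − 29/52) = 10.6 patients, or 10.6/48 = 22%.

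**Step 6: the other reading.** If CRi is taken to include every patient without platelet recovery, CRp patients enter through CRi and the difference is 0.

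**Step 7: effect on the design.** An exact binomial calculation for 18 then 48 patients (stop at 6 or fewer, success at 21 or more) gives type I error 0.1127, power 0.785, early termination probability 0.549 and expected sample size 31.5. The protocol states 0.113, 78.3%, 0.549 and 31.5. These rest on the primary endpoint, which includes CRp, so the secondary formula does not enter them.

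**The case against.** The best counter-argument is that section 6.0 is the only place that defines the categories for this trial, and its CRi wording covers a patient whose platelets have not recovered. On that reading CR + CRi + PR already contains CRp, and only the label is missing. Section 8.1.6 points the same way: it speaks of CRi patients with unrecovered platelets and does not mention CRp. Table 2 shows how earlier studies were tabulated, not how this trial will code. The rate has no test or threshold attached, and the primary endpoint already supplies the like-for-like comparison with the earlier response rates.

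Much of this stands. The loss may be zero, the 33 points cannot be read as a prediction, and no decision depends on the rate. It does not settle the matter, though. Sections 1.1, 3.3, 8.3 and 11.0 all list CRp beside CRi, which would be redundant if CRi absorbed it, and no section says that the inclusive reading governs the secondary rate. An analyst who codes the components named in the primary endpoint and then applies the written formula will drop the CRp patients.

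**Conclusion.** The concern holds and should be fixed. That CRp is absent from both statements of the secondary rate is certain from the text. The numerical effect depends on coding: 0 points if CRi includes CRp, and about 33 points on the Table 2 data if the two are separate. The upper figure assumes this trial would resemble the earlier cohorts in its CRp share and have no PR. The consequence is confined to the descriptive secondary rate and possibly the DoR set.

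**What to change.** In sections 1.2 and 11.0, write the hematologic response rate as CR + CRp + CRi + PR, with each patient counted once. Remission then becomes a subset of response, and the rate is the same whether or not CRi is taken to include CRp. If DoR is computed among responders, state that it uses this same set.

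The cost is adding CRp in two places. Visits, data collection, sample size, stopping rules and dosing text do not change. Section 6.0 need not change for this rate. The overlap between CRp and CRi would remain there, so any report by individual category should say how patients were assigned.
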